16.7 Early Safety Analysis

An early safety analysis will be performed after 6 patients have been accrued to each arm of the study and observed for one cycle. Accrual will be temporarily halted while these patients are evaluated. If 2 or more of the first 6 patients experience a DLT, as defined below, then the dose level will be reduced as defined in Section 8.0 and another six patients will be treated. If < 2/6 patients experience toxicities defined as DLT, then this dose level will be defined as the operational MTD and moved into the expansion portion. Further dose de-escalation to dose level -2 will follow the same guidelines.

Should additional modification be necessary, the study will be closed and evaluated by the study team regarding continuation. Upon determination of the safe dose level, the study will re-open for accrual.

16.8 Data & Safety Monitoring:

- 16.81 The principle investigator(s) and the study statistician will review the study at least twice a year to identify accrual, adverse event, and any endpoint problems that might be developing. The Mayo Clinic Cancer Center (MCCC) Data Safety Monitoring Board (DSMB) is responsible for reviewing accrual and safety data for this trial at least twice a year, based on reports provided by the MCCC Statistical Office.
- 16.82 Adverse Event Stopping Rules: To be evaluated in each arm independently, the stopping rules specified below are based on the knowledge available at study development. We note that the Adverse Event Stopping Rule may be adjusted in the event of either (1) the study re-opening to accrual or (2) at any time during the conduct of the trial and in consideration of newly acquired information regarding the adverse event profile of the treatment(s) under investigation. The study team may choose to suspend accrual because of unexpected adverse event profiles that have not crossed the specified rule below.

Accrual will be temporarily suspended to this study if at any time we observe events considered at least possibly related to study treatment (i.e. an adverse event with attribute specified as "possible," "probable," or "definite") that satisfy one of the following:

- if 3 or more patients in the first 10 treated patients in each arm experience a grade 4 or higher non-hematologic adverse event at least possibly related to treatment.
- if after the first 10 patients in each arm have been treated, 30% of all patients experience a grade 4 or higher non-hematologic adverse event at least possibly related to treatment.

NOTE: Only the arm(s) that crosses the stopping boundary rule will be closed, not then overall study accrual.

We note that we will review grade 4 and 5 adverse events deemed "unrelated" or "unlikely to be related", to verify their attribution and to monitor the emergence of a previously unrecognized treatment-related adverse event.

- 16.9a Results Reporting on ClinicalTrials.gov: At study activation, this study will have been registered within the "ClincialTrails.gov" website. The Primary and Secondary Endpoints along with other required information for this study will be reported on www.ClinicalTrials.gov. For purposes of timing of the Results Reporting, the initial estimated completion date for the Primary Endpoint of this study is 2.5 years after the study opens to accrual. The definition of "Primary Endpoint Completion Date" (PECD) for this study is at the time the last patient registered has been followed for at least 4 months.
- 16.9b Inclusion of Women and Minorities
 - 16.9b1 This study will be available to all eligible patients, regardless of race, gender, or ethnic origin.

- 16.9b2 There is no information currently available regarding differential effects of this regimen in subsets defined by race, gender, or ethnicity, and there is no reason to expect such differences to exist. Therefore, although the planned analysis will, as always, look for differences in treatment effect based on racial and gender groupings, the sample size is not increased in order to provide additional power for subset analyses.
- 16.9b3 The geographical region served by MCCC has a population which includes approximately 3% minorities. Based on prior MCCC studies involving similar disease sites, we expect about 3-5% of patients will be classified as minorities by race and about 33% of patients will be women. Expected sizes of racial by gender subsets are shown in the following table:

Ethnic Category	Sex/Gender				
	Females	Males	Unknown	Total	
Hispanic or Latino	2	3	0	5	
Not Hispanic or Latino	32	65	0	97	
Ethnic Category: Total of all subjects*	34	68	0	102	
Racial Category					
American Indian or Alaskan Native	0	0	0	0	
Asian	0	1	0	1	
Black or African American	1	1	0	2	
Native Hawaiian or other Pacific Islander	0	0	0	0	
White	33	66	0	99	
Racial Category: Total of all subjects*	34	68	0	102	

Accrual Estimates by Gender/Ethnicity/Race

EthnicHispanic or Latino – a person of Cuban, Mexican, Puerto Rico, South or CentralCategories:American, or other Spanish culture or origin, regardless of race. The term "Spanish origin" can also be used in addition to "Hispanic or Latino."
Not Hispanic or Latino

Racial
Categories:American Indian or Alaskan Native – a person having origins in any of the original
peoples of North, Central, or South America, and who maintains tribal affiliations or
community attachment.

Asian – a person having origins in any of the original peoples of the Far East, Southeast Asia, or the Indian subcontinent including, for example, Cambodia, China, India, Japan, Korea, Malaysia, Pakistan, the Philippine Islands, Thailand, and Vietnam. (Note: Individuals from the Philippine Islands have been recorded as Pacific Islanders in previous data collection strategies.)

Black or African American – a person having origins in any of the black racial groups of Africa. Terms such as "Haitian" or "Negro" can be used in addition to "Black or African American."

Native Hawaiian or other Pacific Islander – a person having origins in any of the original peoples of Hawaii, Guam, Samoa, or other Pacific Islands.

White – a person having origins in any of the original peoples of Europe, the Middle East, or North Africa.

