8.12 AZD1775 single agent (Arm C)

Dose	AZD1775
0*	200 mg PO daily days 1-5, 8-12, 15-19, 22-26

	200 mg PO daily days 1-5, 8-12, 15-19
1.0**	or
-1a	further reduction to 200 mg PO daily days 1-5 & 8-
	12 as tolerated
	100 mg PO daily days 1-5, 8-12, 15-19, 22-26
-1b**	
	100 mg PO daily days 1-5 & 8-12
2	
-2	

*Presumed starting dose of Expansion Portion.

**If at dose -1a leukemia breakthrough is observed, dose modification level -1b can be explored if continuous treatment may bring clinical benefit.

Note: Further dose modifications can be made, i.e. 150 mg PO daily days 1-5, 8-12, 15-19.

The above dose modification tables consider the fact that at present it is not clear if dose (Cmax) or continuous (length of therapy, AUC, trough) dosing of AZD1775 will achieve better disease control, hence the dose modification scheme (i.e. compared to hydroxyurea experience and titration).

- 8.2 A new course of treatment may begin on the scheduled Day 1 of a new cycle if:
 - AZD1775 or AraC related adverse event that may have occurred has resolved to \leq Grade 2 severity, except hematological adverse events for WBC, ANC, Platelets and Hemoglobin, or per table 8.3 guidelines.

If these conditions are not met on scheduled Day 1 of a new cycle, the subject will be evaluated as clinically indicated (i.e. weekly but at least every other week) and the new cycle of treatment will not be initiated until the adverse event has resolved as described above. Treatment can be continued on the drug that is not associated with the adverse event at the start of the following cycle and the drug associated with the adverse event may be reintroduced when the adverse event resolves to \leq Grade 1 if the treating physician feels that the patient will derive benefit from continued AraC or AZD1775 alone.

NOTE: If the patient experiences a significant adverse event requiring a dose reduction at the start of the next cycle, then the dose will remain lowered for that entire subsequent cycle. If that cycle is completed with no further adverse events >Grade 2, then the dose may be increased, at the investigator's discretion, one level at a time, in the following cycles.

8.3 Dose modification table for adverse events felt to be at least possibly related to AZD1775*** or AraC

→ → Use the NCI Common Terminology Criteria for Adverse Events (CTCAE) version 4.0* unless otherwise specified \leftarrow ←

CTCAE System/Organ/Class (SOC)	ADVERSE EVENT	AGENT	ACTION**					

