BASED ON INTERVAL ADVERSE EVENT***								
Blood and Lymphatic System Disorders	Febrile neutropenia ≥ Grade 3	AZD1775	May omit dose until fever has resolved or returned to baseline. Dose to be restarted at same dose level. Treating physician may discuss possible dose reduction with one of the study chairs after the patient has completed 2 cycles. If clinical benefit is derived, AZD1775 may be continued if the infection is managed/controlled with appropriate medical intervention.					
Investigations	Neutrophil & Platelet count decrease \geq grade 4 NOTE: only applicable for patients with absolute neutrophil count (ANC) of \geq 1000mm³ and platelet count > 100,000/mm³ at baseline (i.e. MDS patients)	AZD1775	Omit dose until ANC and/or platelets have recovered to \leq grade 2. If clinical benefit is derived, AZD1775 may be continued if not recovered to \leq grade 2 after discussion of treating physician and study chair.					
Investigations	Creatinine increased Grade 2	AZD1775 AraC	 Omit dose until resolved to ≤ grade 1, then: If resolved in ≤ 7 days, then maintain dose level If resolved in > 7 days, then decrease by 1 dose level [If clinical benefit is derived, AZD1775 may be continued if the renal function is elevated but stable] Continue treatment at current dose level 					
	Creatinine increased Grade 3 and 4	AZD1775 AraC	Omit dose until resolved to \leq grade 1, then decrease dose by 1 dose levelOmit dose until resolved to \leq grade 1, then decrease dose by 1 dose level					
→ \rightarrow Use the NCI Common Terminology Criteria for Adverse Events (CTCAE) version 4.0* unless otherwise specified \leftarrow \leftarrow								
--	---	-------------------------	---	--	--	--	--	--
CTCAE System/Organ/Class (SOC)	ADVERSE EVENT	AGENT	ACTION**					
Investigations	Blood bilirubin increased ≥ Grade 3	AZD1775 AraC	 Omit dose until resolved to ≤ grade 1, then: If resolved in ≤ 7 days, then maintain dose level If resolved in > 7 days, then decrease by 1 dose level Continue treatment at next lower dose 					
	Blood bilirubin increased Grade 4	AZD1775 AraC	level Omit dose until resolved to ≤ grade 1, then decrease dose by 1 dose level Continue treatment at Dose level -1once					

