10.41 Special Situations for Expedited Reporting

Exceptions to Expedited Reporting and Submission of Notification Forms: EXPECTED Serious Adverse Events

An expedited report or notification form may not be required for specific Grade 1, 2 and 3 Serious Adverse Events where the AE is **EXPECTED**. Any protocol specific reporting procedures MUST BE SPECIFIED BELOW and will supercede the standard Expedited Adverse Event Reporting Requirements (Note: These adverse events must still be reported through the routine reporting mechanism [i.e. Nadir/adverse events form]; see footnote 1):

NOTE: These only apply to those events that are not attributed to AZD1775 (Unlikely or Unrelated as defined in Section 10.3).

System Organ Class (SOC)	Adverse event/ Symptoms	CTCAE Grade at which the event will not be expeditedly reported ¹
General disorders and administrations site conditions	Fatigue	Grade 3
	Nausea	
Gastrointestinal	Vomiting	Grade 3
Disorders	Diarrhea	
Investigations	Neutrophil count decreased	Grade 3 and Grade 4
	White blood cell count decreased	Glade 5 and Glade 4
	Platelet count decreased	
Blood and lymphatic	Anemia	Grade 3 and Grade 4
system disorders	Febrile Neutropenia (in AML patients only)	Grade 3 and Grade 4

1. These exceptions only apply if the adverse event does not result in hospitalization. If the adverse event results in hospitalization, then the standard expedited adverse events reporting requirements must be followed.

Specific protocol exceptions to expedited reporting should be reported expeditiously by investigators **ONLY** if they exceed the expected grade of the event.

10.5 **Other Required Reporting**

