10.52 Death

Any death occurring within 30 days of the last dose, regardless of attribution to an agent/intervention under an IND/IDE requires expedited reporting within 24-hours.

Any death occurring greater than 30 days with an attribution of possible, probable, or definite to an agent/intervention under an IND/IDE requires expedited reporting within 24-hours.

Reportable categories of Death

- Death attributable to a CTCAE term.
- Death Neonatal: A disorder characterized by cessation of life during the first 28 days of life.
- Death NOS: A cessation of life that cannot be attributed to a CTCAE term associated with Grade 5.
- Sudden death NOS: A sudden (defined as instant or within one hour of the onset of symptoms) or an unobserved cessation of life that cannot be attributed to a CTCAE term associated with Grade 5.
- Death due to progressive disease should be reported as Grade 5 "Neoplasms benign, malignant and unspecified (incl cysts and polyps) Other (Progressive Disease)" under the system organ class (SOC) of the same name. Evidence that the death was a manifestation of underlying disease (e.g., radiological changes suggesting tumor growth or progression: clinical deterioration associated with a disease process) should be submitted.

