use of Atorvastatin is therefore prohibited in the current study. Other drugs where the disposition is mediated via BCRP should be administered with caution, dose modification considered or substituted by an alternative drug (Appendix VI).

- AZD1775 has been shown to be an inhibitor or MATE1 and MATE2K transporters. A drug interaction with substrates of either transporter cannot be ruled out, the most important substrate known to date being **metformin**.
- Herbal preparations/medications are not allowed throughout the study. These herbal medications include, but are not limited to: St. John's wort, kava, ephedra (ma huang), gingko biloba, dehydroepiandrosterone (DHEA), yohimbe, saw palmetto, and ginseng. Patients should stop using these herbal medications 14 days prior to first dose of AZD1775.
 - 15.17 **Known potential toxicities**: Based on the preliminary safety data available, the most frequent adverse events observed were blood and lymphatic disorders (anemia, febrile neutropenia), gastrointestinal disorders (diarrhea, vomiting, nausea, abdominal pain, constipation), general disorders and administration site conditions (fatigue, fever, chills), and investigation findings (thrombocytopenia, neutropenia, hematology and serum chemistry).
 - 15.18 **Drug procurement:** Drug will be provided by AstraZeneca.

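### The numeric stopping boundaries in 16.82 leave out hematologic events even at Grade 5, so a treatment-related death coded to a hematologic term may not count toward mandatory suspension (minor, cheap to fix)

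*Combined protocol and SAP*

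**What the plan says.** Section 16.82 gives two numeric rules, applied to each arm separately and limited to events rated possibly, probably or definitely related.

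- First 10 patients: suspend "if 3 or more patients in the first 10 treated patients in each arm experience a grade 4 or higher non-hematologic adverse event".
- After the first 10: suspend if "30% of all patients experience a grade 4 or higher non-hematologic adverse event at least possibly related to treatment".

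The section also leaves room for judgment: "The study team may choose to suspend accrual because of unexpected adverse event profiles that have not crossed the specified rule below". It adds a review of Grade 4 and 5 events, but only those rated unrelated or unlikely to be related.

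Neither 16.82 nor any other section defines non-hematologic. Two parts of the protocol bear on its meaning.

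- **By list.** Section 8.2, on starting a new cycle, makes an exception in these words: "except hematological adverse events for WBC, ANC, Platelets and Hemoglobin".
- **By organ class.** Table 8.3 places "Febrile neutropenia ≥ Grade 3" under blood and lymphatic system disorders. The exceptions table in 10.41 puts "Febrile Neutropenia (in AML patients only") in the same class. Section 15.17 says that "the most frequent adverse events observed were blood and lymphatic disorders (anemia, febrile neutropenia") among others.

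On deaths, 10.52 states: "Any death occurring within 30 days of the last dose, regardless of attribution to an agent/intervention under an IND/IDE requires expedited reporting within 24-hours". Deaths are coded to a CTCAE term where one applies (10.52, 10.613), so a death can carry a hematologic term.

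**The concern.** Setting ordinary cytopenias aside is sensible in AML and MDS, and it is deliberate (1.52, 7.4). The difficulty is that the restriction has no upper limit on grade. It removes a fatal event with a hematologic term in the same way as a low neutrophil count.

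The rule exists to force a pause without debate. If two careful readers can disagree on whether a related fatal febrile neutropenia counts, it does not do that for this event. On the reading that excludes it, no number of such deaths would trip either boundary. After the first cycle of the safety portion, when the DLT rule no longer applies, 16.82 holds the only numeric safety limit.

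**Working it through.** **Reproducing a stated figure.** The plan gives no operating characteristics for 16.82, so there is none to reproduce.

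**Step 1: how one related fatal febrile neutropenia is counted.**

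| Reading of hematologic | Basis | Adds to the 3-of-10 count | Adds to the 30% count |
|---|---|---|---|
| Blood and lymphatic disorders class | Table 8.3, 10.41, 15.17 | 0 | 0 |
| WBC, ANC, platelets, hemoglobin | 8.2 | 1 | 1 |

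The gap is narrow. A related death coded to sepsis, to bleeding in another organ class, or to death not otherwise specified is non-hematologic on either reading and already counts.

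**Step 2: the boundary in patients.** Suspend at 3 or more up to n = 10, then at 0.3n rounded up: 4 for n = 11–13, 5 for 14–16, 6 for 17–20, 7 for 21–23. Maximum planned accrual is 22 in Arms B and C and 23 in Arm A (16.22, 16.23).

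**Step 3: what the fix does to the chance of a pause.** The documents give no event rates, so all rates here are assumptions. Let pn be the share of patients with a related non-hematologic Grade 4+ event and pd the share with a related death coded as hematologic. If the two are independent, the share counted after the fix is

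p = 1 − (1 − pn)(1 − pd).

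For pn = 0.10 and pd = 0.05, p = 1 − 0.90 × 0.95 = 0.145. A patient-by-patient binomial recursion against the Step 2 boundary gives the chance of crossing by n = 22:

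| pn | pd = 0 | 0.01 | 0.02 | 0.05 |
|---|---|---|---|---|
| 0.05 | 0.012 | 0.020 | 0.030 | 0.075 |
| 0.10 | 0.080 | 0.099 | 0.121 | 0.198 |
| 0.15 | 0.215 | 0.243 | 0.273 | 0.367 |

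Under the current wording, with such deaths excluded, each row stays at its pd = 0 value. For Arm A at n = 23 and pn = 0.10 the row is 0.080, 0.100, 0.122, 0.200.

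**Step 4: overlap.** The rule counts patients, so someone who already has a counted event adds nothing by dying. At pn = 0.10 and pd = 0.05:

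- half overlap: p = 0.10 + 0.5 × 0.05 = 0.125, crossing 0.139
- 80% overlap: p = 0.10 + 0.2 × 0.05 = 0.11, crossing 0.101
- full overlap: p = 0.10, crossing 0.080, no change

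The recursion treats each event as known at once. In practice a pause would come later.

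**The case against.** The strongest objection is that sorting by organ class cannot be what the protocol means. Table 8.3, 10.41 and 10.6 list neutrophil and platelet decreases under Investigations. Applied consistently, that sorting would count expected Grade 4 cytopenias as non-hematologic and defeat the purpose of the exclusion: if an assumed 30% of patients had them, the 3-of-10 boundary would be crossed with probability 0.62. The only list in the protocol, in 8.2, would already count a fatal febrile neutropenia. This stands in part. It shows that organ class is a poor guide, and that adding a clause on deaths without defining the term would leave the ambiguity in place. It does not settle the reading, because 8.2 governs retreatment and 16.82 does not refer to it.

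The second objection is that other safeguards apply: death reporting within 24 hours, DSMB review at least twice a year, freedom to suspend accrual or adjust the rule, and the 2-of-6 DLT rule in 16.7. These are real, but none sets a number for these deaths. The suspension clause concerns unexpected profiles. Febrile neutropenia is listed in 15.17, so it is expected by nature, although 10.2 also refers to severity and a fatal case might qualify that way. The DLT rule covers only cycle 1 of the safety portion and sets myelosuppression aside without saying whether febrile neutropenia is included.

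A reader might infer that treatment-related deaths go unmonitored, or that the drug has already caused deaths of this kind. The documents support neither. The fatal events named for PN001 in 1.41 are neoplasm progression, renal failure, respiratory failure, pneumonia, hypoxia and lung infiltration. None carries a hematologic term of the kind at issue, and any judged related would not be lost through this gap.

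**Conclusion.** The point holds as a minor, inexpensive improvement. No stated figure is wrong. Both mandatory boundaries exclude hematologic events at all grades, so a related death under a hematologic CTCAE term may not count. Whether it does depends on an undefined word.

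The effect is modest and rests on assumed rates. At a 10% non-hematologic rate, the fix raises the chance of an arm-level pause by 22 patients by about 0.02 to 0.04 if 1% to 2% of patients have such a death. At 5% the rise is about 0.12 under independence, 0.06 at half overlap and nil at full overlap. A death standing alone crosses no boundary before or after the fix, but after it a death could be the event that completes one.

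**What to change.** Make two changes in 16.82 and keep the 3-of-10 and 30% boundaries.

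1. In both bullets, count a patient who has, at least possibly related to treatment, either a Grade 4 or higher non-hematologic event or a Grade 5 event under any CTCAE term.
2. State that hematologic means decreases in WBC, ANC, platelets or hemoglobin (the 8.2 list), wherever CTCAE files them. Non-fatal cytopenias then stay excluded.

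The second change also makes a related Grade 4 febrile neutropenia count, and the figures above do not include that. If it is not wanted, febrile neutropenia can be added to the hematologic list; the Grade 5 clause would still capture fatal cases.

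No new data are needed. Grade 5 events and their attribution are already collected (10.52, 10.613), and 16.41 already tabulates Grade 4 or higher events of both kinds. The price is a short text amendment and slightly more temporary pauses, each confined to the arm that crosses.

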17.0 Pathology Considerations: None

18.0 Records and Data Collection Procedures

18.1 Submission Timetable (need to be updated)

Initial Material(s)

Case Report Form (CRF)	Active-Monitoring Phase (Compliance with Test Schedule Section 4.0)
On-Study	
Baseline Adverse Event	
Measurement - Baseline	
Bone marrow biopsy report with	
cytogenetics and/or FISH	≤ 2 weeks after registration
Research Blood Submission (see Section	
14.0)	
Research Bone Marrow Aspirate Submission	
(see Section 14.0)	
Research Saliva Submission -Baseline	
Patient Questionnaire Booklet	≤ 2 weeks after registration – Patient questionnaire booklet
	must be used; copies are not acceptable for this submission.
Patient Questionnaire Booklet Compliance	≤ 2 weeks after registration – This form must be completed
	only if the Patient Questionnaire Booklet contains absolutely
	NO patient provided assessment information.
End of Active Treatment/Cancel Notification	Submit ≤2 weeks after registration if withdrawal/refusal
	occurs prior to beginning protocol therapy

Test Schedule Material(s)

CRF	Active-Monitoring Phase (Compliance with Test Schedule Section 4.0)				
	At each evaluation during treatment	At end of treatment			
Evaluation/Treatment	Х	Х			
Nadir/Adverse Event	Х	Х			
Measurement	X^3	X^3			
Bone marrow biopsy report with cytogenetics and/or FISH	X ³	X ³			
Patient Questionnaire Booklet	X ¹	Х			

	Active-Monitoring Phase (Compliance with Test Schedule Section 4.0)				
CRF					
	At each evaluation during treatment	At end of treatment			
Patient Questionnaire Booklet Compliance	X ²	Х			
Research Blood Submission	X (see Section 14.0)	Х			
Research Bone Marrow Aspirate Submission	X (see Section 14.0)				
PK Specimen Submission (Cycle 1)	X (see Section 14.0) (Cycle 1 only)				
PK Specimen Submission (Cycle 2+)	X (see Section 14.0) (Cycle 2+)	Х			
End of Active Treatment/Cancel Notification		Х			
Notification–Grade 4 or 5 Non-AER Reportable Events/Hospitalization	At each occurrence (see Section 10.0)				
ADR/AER	At each occurrence (see Section 10.0)				

1. Patient questionnaire booklet **must** be used; copies are not acceptable for this submission. To be completed prior to treatment every cycle.

2. This form must be completed only if the patient questionnaire booklet contains absolutely NO patient provided assessment information.

3. Submit copy of documentation of response (CR, CRi, PR, CI, MLFS, Marrow CR) or PD/Relapse/Fail/Failure, Attention

Follow-up Material(s)

	Event Monitoring Phase ¹				
CRF	q. 3 months until PD^2	At PD ²	After PD q. 6 mos.	Death	New Primary
Event Monitoring	Х	Х	Х	Х	At each occurrence

1. If a patient is still alive 2 year after registration, no further follow-up is required.

2. Submit copy of documentation of response or progression to the MCCC Operations Office, Attention:

